3.4 Sample size calculation

Our study is powered to answer the main research question: "Do more children with MIS-C or post-COVID condition have deleterious variants in immunological genes than exposed controls?" To analyze the genetic data from the case-control study, we will use rare-variant collapsing analyses, as reviewed by Povysil, et al [35] (see Chapter 9 (Statistical Analysis) for details).

Power analysis using Monte Carlo simulation:

In a previous study in MIS-C, 17% of patients (3/18) had deleterious variants in immunological genes. In controls, the prevalence of (predicted) loss of function variants in our gene-set is about 3.7% (according to gnomAD v. 2.1.1 data, using a minor allele frequency of <0.00001). This yields an odds ratio of 5.2 ($3/18 * 0.963 / (0.037 * 15/18)$). **Therefore, for the power analysis, we conservatively assume that cases have more qualifying variants than healthy controls, with an odds ratio of 4.** We found the 'normal variation' in controls to be present in all the clusters. We assume that the 'background variation' in cases is similarly spread out over the clusters.

The simulations have been run 1000x, with 100 cases and 200 controls.

Causative variants should cluster together

We hypothesize that causative genetic variants that are more prevalent in cases are functionally related. They underly a pathogenic mechanism and should cluster together. Therefore, we assume that excess variants in cases cluster together, either in one or in two clusters. See Chapter 9 (Statistical Analysis) for details on the cluster analysis.

Power of 80% assuming an odds ratio of 4 and one cluster affected

Individuals are positive if they have at least one qualifying variant in at least one gene. The **overall positive rate** is the proportion of simulations in which the Fisher exact P value comparing positive cases and controls is <0.05 . A genecluster-by-individual collapsing matrix is constructed. For every simulated case or control it is assessed if at least one of the clusters is affected. A Fisher exact test is calculated for each simulation. The **cluster true positive rate** is the proportion of simulations in which both the overall Fisher exact P-value and the cluster-specific Q-value (using Benjamini-Hochberg FDR) are <0.05 .

Cluster	Overall positive rate	Cluster true positive rate	Cluster false positive rate
1	0.823	0.807	0.014
2	0.814	0.791	0.008
3	0.812	0.803	0.014
4	0.833	0.816	0.012
5	0.806	0.772	0.002

Assuming an odds ratio of 4 the power for an overall positive result is above 80%. The power to detect the responsible cluster is around 80%. The false positive rate is below $\alpha = 0.05$.

Detection of at least one cluster assuming two clusters are affected

Assuming an odds ratio of 4 and two clusters affected, the power for an overall positive result is above 80%. The power to detect at least one of the two responsible clusters is around 70%. The false positive rate is below $\alpha = 0.05$.

Clusters	Overall positive rate	One cluster positive rate	Two cluster positive rate	Cluster false positive rate
1 + 2	0.819	0.710	0.409	0.009
1 + 3	0.835	0.726	0.426	0.013
1 + 4	0.842	0.698	0.416	0.004
1 + 5	0.837	0.714	0.35	0.005
2 + 3	0.814	0.692	0.363	0.003
2 + 4	0.823	0.665	0.362	0.004
2 + 5	0.844	0.638	0.292	0.000
3 + 4	0.833	0.700	0.387	0.010
3 + 5	0.809	0.659	0.304	0.005
4 + 5	0.832	0.66	0.307	0.003

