7.3.2 Whole exome sequencing and data analysis

The saliva collection kits can be returned via regular mail and will be stored at room temperature (15-30°C) until analysis.

The collected saliva samples will be sent to GenomeScan (an ISO/IEC 17025 accredited laboratory). The samples will only contain the study specific number of the participant. GenomeScan will do the DNA isolation. DNA sequencing will be done using the Agilent SureSelect Human All Exon V7 kit, using Illumina

NovaSeq6000 sequencing, Paired-End, 150 bp. Per sample we will obtain ~12 Gb, 40 million Paired-End reads.

In a NEN-EN-ISO 15189 accredited genome diagnostic center existing bio-informatic pipelines and databases will be used. Sequenced reads will be mapped to the Genome Reference Consortium Human Build 37 (GRCh37 or hg19) reference genome. Variants are classified according the guidelines as established by the American College of Medical Genetics and Genomics and the Association for Molecular Pathology guideline (33), similar to the approach in our Genetics first – primary immunodeficiencies study (34, 35).

We will make use of publicly available reference exome data sets (including GnomAD database, GoNL database) to determine the frequency of genetic variants in reference populations (36). We will include only protein-altering variation with a presumed high impact on protein function, including protein-truncation (stop or frameshift mutations) or disturbance of canonical splice-sites. In-frame insertions/deletions and missense mutations will be scored, and variants with a 'likely' estimated impact on protein functioning (CADD>15) will be included in the analysis (37, 38).

Class	Description	Probability of being Pathogenic
5	Definitely Pathogenic	>0.99
4	Likely Pathogenic	0.95–0.99
3	Uncertain	0.05–0.949
2	Likely Not Pathogenic or of Little Clinical Significance	0.001–0.049
1	Not Pathogenic or of No Clinical Significance	<0.001

Data collection

Clinical data:

- Clinical data of the MIS-C and post-covid condition patients has already been collected in the existing studies. We will ask consent of the participants to use this data to be able to compare genetic and clinical data.

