9. STATISTICAL ANALYSIS

9.1 Primary study parameter(s)

The first steps in the analysis will be to **identify the qualifying variants**, as previously reviewed by Povysil *et al.* (40).

- 1) **Sample QC:** Obtained genotypes will be used to investigate the relatedness between samples. Samples that are too interrelated, possibly due to unknown relatedness, are excluded for further analysis as this violates the assumption of independence between samples. Likewise, samples that are too unrelated, possibly due to an unknown admixture, are excluded for further analysis as this would yield an inflated estimate of rare variants, that are in fact mostly benign population-specific variants.
- 2) **Variant QC:** For each contrast, variants are scrutinized for differences in coverage and other variant QC measures. Variants with significant differences in QC between cases and controls are discarded.
- 3) **Variant filtering:** This will enrich the subsequent gene-collapsing analyses for rare and presumably deleterious variation that confers disease risk, while minimizing the impact of neutral background variation. The goal is to optimize statistical power to test for involvement in the pathophysiology of MIS-C. For this purpose, we will filter for rare variation in external reference cohorts (gnomAD, MAF<0.00001). In addition, we will include only protein-altering variation with a presumed high impact on protein function, including protein-truncation (stop or frameshift mutations) or disturbance of canonical splice-sites. In-frame insertions/deletions and missense mutations will be scored, and variants with a 'likely' estimated impact on protein functioning (CADD>15) will be included in the analysis (37, 38).

Qualifying variant selection					
variant	gene	sample	filters		
			variant quality	variant annotation	external MAF
V1	G1	S1	ü	ü	ü
V1	G1	S2	û	ü	ü
V3	G2	S3	ü	ü	û
V4	G3	S3	ü	ü	ü
V5	G3	S4	ü	û	ü
V6	G4	S5	ü	ü	ü
...				...	
Vn	G453	S1	ü	ü	ü

[figure not shown]
Example of Qualifying Variant selection table, adapted from Povysil *et al.*, (40)

Cluster analysis of IEI gene-set

We have done a cluster analysis on the IEI-gene set. Leading Eigen cluster analysis was done based on known and predicted protein-protein interactions, using STRINGdb version 11.5 (41, 42). The interactions include direct (physical) and indirect (functional) associations. We included all interactions of medium confidence (cutoff = 0.4) and subsequently assigned

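### The roughly 80% power in section 3.4 rests on a loss-of-function carrier rate, but the planned test counts a broader variant class, so that power is not established for it

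*Protocol*

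**What the plan says.** Three parts of the protocol bear on this.

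- **Power inputs (section 3.4).** The control rate is given as "In controls, the prevalence of (predicted) loss of function variants in our gene-set is about 3.7" per cent, at a gnomAD minor allele frequency below 0.00001. The case figure is "In a previous study in MIS-C, 17% of patients (3/18) had deleterious variants in immunological genes". Together they give an OR of 5.2, and the section then states: "we conservatively assume that cases have more qualifying variants than healthy controls, with an odds ratio of 4". On group size: "The simulations have been run 1000x, with 100 cases and 200 controls".
- **What counts as positive (section 3.4).** "Individuals are positive if they have at least one qualifying variant in at least one gene". Power for the overall comparison is then the share of simulated studies whose Fisher test on carriers reaches P<0.05.
- **What qualifies (sections 7.3.2 and 9.1).** Truncating and canonical splice-site variants qualify. In addition, "In-frame insertions/deletions and missense mutations will be scored", and those with a likely impact "on protein functioning (CADD>15) will be included in the analysis". Section 9.1 applies the same frequency cut-off as 3.4 and collapses all qualifying variants.

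The protocol gives no carrier rate for this wider set and specifies no primary test restricted to loss-of-function variants.

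**The concern.** The control rate in the simulation and the variable to be tested are described for different variant classes. The frequency cut-off is the same in both places, so adding in-frame and missense variants can leave the control carrier rate unchanged or raise it, but cannot lower it. The gene set is numbered up to G453 in the section 9.1 tables, so there is ample room for additional carriers.

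The OR has a related weakness. Its numerator is patients with deleterious variants, of types the protocol does not state. Its denominator is loss-of-function carriers. Reducing 5.2 to 4 allows for optimism in the estimate, but it does not put the two rates on one definition.

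Section 3.4 presents the study as powered for its main question. A reader of the results would attach about 80% power to a test for which that figure was not derived, and would weigh a non-significant overall result accordingly.

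**Working it through.** **Inputs from section 3.4:** control rate p0 = 0.037; case figure 3/18; OR 4; 100 cases and 200 controls; Fisher exact P<0.05. Sidedness is not stated. Two-sided is used here because it reproduces the plan's figures (0.826), whereas one-sided gives 0.864.

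**Step 1. Reproduce the plan.**
- OR = (3/18 × 0.963)/(0.037 × 15/18) = 5.2, as stated.
- At OR 4, case odds = 4 × 0.037/0.963 = 0.1537, so p1 = 0.1537/1.1537 = 0.133.
- Exact Fisher power, by enumerating both binomials, is **0.826**. The plan states 0.806 to 0.833 with one cluster affected.
- A five-cluster simulation with equal background per cluster and Benjamini-Hochberg adjustment gives 0.822 overall and 0.800 for the affected cluster. The plan states 0.772 to 0.816 for the latter.

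The arithmetic is therefore sound for its own inputs, and those inputs are the loss-of-function rate with OR 4.

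**Step 2. Replace the control rate.** The documents do not give the rate for the full section 9.1 set, so two assumptions are shown.

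*Assumption A: OR 4 holds for the full set.* With control carriage c, case odds = 4c/(1−c).

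| Control carriage c | Case carriage | Power |
|---|---|---|
| 3.7% | 13.3% | 0.826 |
| 5% | 17.4% | 0.91 |
| 10% | 30.8% | 0.99 |

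*Assumption B: the excess stays at 13.3% against 3.7%, and the added variants are neutral, independent and carried by a proportion b of both groups.* Control rate = 1−(1−0.037)(1−b); case rate = 1−(1−0.1332)(1−b).

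| Added carriage b | Control rate | Case rate | OR | Power |
|---|---|---|---|---|
| 0.5% | 4.2% | 13.8% | 3.66 | 0.80 |
| 1% | 4.7% | 14.2% | 3.38 | 0.77 |
| 5% | 8.5% | 17.7% | 2.30 | 0.59 |
| 10% | 13.3% | 22.0% | 1.83 | 0.44 |
| 20% | 23.0% | 30.7% | 1.48 | 0.28 |

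In table A the first column is total control carriage. In table B it is only the added part, so equal percentages in the two tables do not describe the same situation.

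**Step 3. OR needed for 80% power.** By the same exact calculation it is about 3.4 at 5% control carriage, 2.65 at 10% and 2.2 at 20%. An OR of 4 is thus more than the test needs at higher carriage, but the OR under assumption B falls faster than the requirement does.

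**The case against.** The strongest objection is that section 3.4 states the OR of 4 for qualifying variants, not for loss-of-function variants. If that assumption is accepted for the full set, a higher control rate helps and the stated power is an understatement. Assumption B is also an extreme: it gives every added variant no effect, although the CADD threshold is meant to select damaging variants. Section 1 names the three genes found in the 18 patients but not the variant types. If any were missense, the added class carries signal. All of this stands, and it rules out a one-directional claim.

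It does not rescue the input. The only support offered for the OR is 3/18 against 3.7%. Keeping OR 4 at 10% control carriage requires 30.8% of cases to be carriers, and the only case figure given is 16.7%. That figure comes from 18 patients, so a higher rate is not excluded, but none is argued for.

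Two stronger readings are tempting, and the documents support neither.

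- A reader might infer that the design lacks 80% power, or that a null result is likely. Both require the carrier rate and the effect size for the full set, and neither is given.
- A reader might hold case carriage at 16.7% while raising control carriage, and conclude that the OR falls to 1.8 at 10% and to 1.0 at 16.7%. That adds background to controls only, whereas section 3.4 assumes background variation in cases as well. Under assumption B the OR at 10% control carriage is 2.11.

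It is also possible that the 3.7% was in fact counted on the full set and loosely labelled. Section 3.4 does not say so; if it was, correcting the label would resolve the control rate.

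**Conclusion.** The concern holds in a limited form. As written, the control rate in 3.4 belongs to a narrower class than the one 7.3.2 and 9.1 collapse and test, and the OR compares two rates not shown to share a definition. The figure of about 80% is correctly computed from those inputs but is not established for the planned test.

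The direction of the error is open. Power is 0.91 to 0.99 at 5% to 10% control carriage if OR 4 holds for the full set. It is 0.77 down to 0.28 for added carriage of 1% to 20% if the added variants are neutral and equally common in both groups. On the second assumption the margin is thin: 0.5% added carriage already brings power down to 0.80. The carriage values and the behaviour of the added variants are assumptions; the group sizes, the 3.7%, OR 4 and the test come from section 3.4.

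**What to change.** In section 3.4:

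1. Take the control carrier rate from gnomAD for exactly the section 9.1 qualifying-variant set: truncating, canonical splice, and in-frame or missense with CADD>15, at the stated frequency cut-off.
2. Justify the effect size on that same definition, saying which variant types the 3/18 patients carried. Include a scenario in which the added in-frame and missense variants are neutral background.
3. Rerun the existing simulation and replace the overall and cluster power figures.

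If the sponsor prefers, loss-of-function variants could instead be pre-specified as the primary set, with the CADD>15 set secondary. That aligns the tested set with the 3.7%, but it narrows the main question and leaves damaging missense variants to a secondary analysis. It also does not repair the OR, so an effect size justified for loss-of-function variants would still be needed.

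The cost is a reference-database query, a rerun of an existing simulation and revised wording, with no new participants or samples. The downside is that the restated power may be lower. The choice of primary set should be fixed before case and control variants are compared.

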4. TREATMENT OF SUBJECTS

Not applicable

5. INVESTIGATIONAL PRODUCT

Not applicable

6. NON-INVESTIGATIONAL PRODUCT

We will use self-collection kits to collect the saliva:

<https://www.dnagenotek.com/ROW/products/collection-human/oragene-dna/500-series/OG-500.html>

For children unable to self-collect saliva, a kit for assisted collection will be used:

<https://www.dnagenotek.com/ROW/products/collection-human/oragene-dna/500-series/OG-575.html>

7. METHODS

7.1 Study parameters/endpoints

7.1.1 Main study parameter/endpoint: WES to detect rare, high impact genetic variants

First, we will evaluate if some children with MIS-C or post-COVID condition have a previously unidentified inborn error of immunity (IEI)

We will use existing diagnostic algorithms to diagnose monogenic inborn errors of immunity in MIS-C or post-COVID condition cases. This means that here, **we will restrict our analysis to pathogenic (class 5) or likely pathogenic (class 4) variants** (as established by the American College of Medical Genetics and Genomics and the Association for Molecular Pathology guideline (33)) **in genes known to be associated with monogenic inborn errors of immunity (IUIS IEI gene set).**

Next, we will do a case-control rare variant association study.

In the subsequent case-control analysis we will focus on determining if a larger proportion of cases with MIS-C or post-COVID condition have rare and presumably deleterious variants in immunological genes than children with an asymptomatic or mild infection.

7.1.2 Secondary study parameters/endpoints: Clinical characteristics and long-term effects of pediatric COVID-19 and MIS-C

We will describe the clinical characteristics of children hospitalized with COVID-19 or MIS-C. Also, we will evaluate the long-term effects of pediatric COVID-19 and MIS-C. A detailed description of the clinical course of MIS-C and post-COVID condition will enable us to make subgroups of patients. For example, children with MIS-C who need inotropic support vs. those who do not. For this purpose, we will use available data from our ongoing nation-wide cohort study of children with COVID-19 or MIS-C in Dutch hospitals (Clinical features of COVID-19 in Pediatric Patients; COPP-study and COPP-IMM study; WHO-CRF with additions). Inclusion in this study is ongoing in 53 hospitals.

To evaluate the long-term effects of pediatric COVID-19 and MIS-C, we will analyze data from the ongoing follow-up study COPP2 and the PICU follow-up data. Children included in the COPP-study are invited at six to twelve months for a multi-disciplinary study visit. Patient reported outcome measures (PROMs) will be collected, as well as an assessment of exercise tolerance, lung function, smell and taste testing, neurocognitive testing and an immunological assessment. Children referred to our clinic because of post-COVID condition will be assessed in a similar manner. We will compare this with data from the PoCoCoChi study ("Post Corona Complaints in Children"), in which children tested for SARS-CoV-2 at a GGD test location Kennemerland with a negative or positive test result are prospectively evaluated for long-term effects. Other reference groups of children will be identified from the ongoing home studies including COKids, CORNathuis and SARSLIVA.

7.1.3 Other study parameters: integrated analysis and aim to identify therapeutic targets

1. We will do targeted immunological studies to validate the results from the genetic study. For example, if we find that a child has a novel variant that is classified as class IV (likely pathogenic) in a specific gene normally present in T-cells, we will first evaluate if this gene is expressed (RNA and/or protein) in T-cells of the patient. If there is no RNA/protein expression, this further supports the pathogenicity of the novel variant. If we find that more cases have predicted loss of function variants in cluster 1 (complement activation), we will measure the levels of complement proteins in serum. This can be done in: a) the cases with predicted loss of function variants and compare this with controls; and b) also be evaluated in cases without genetic perturbations in complement genes to evaluate if these are functionally impaired (by acquired or intronic variants).
2. We will evaluate if genetic risk factors aggregate in specific subgroups of patients. For example, we will compare if more MIS-C cases who have cardiac involvement (more severe phenotype) have genetic variants in immunological genes than MIS-C cases who do not need inotropic support.
3. Identification of therapeutic targets: For example, if we find more cases than controls have variants in cluster 2 (intracellular signaling pathways), we will test pharmacological agents that influence these pathways in cells of cases and controls (for example JAK inhibitors).

7.2 Randomisation, blinding and treatment allocation

Not applicable

7.3 Study procedures

7.3.1 Recruitment and sampling

Recruitment: Invitation by email

- Participants will be invited by email through the study in which they have participated before
- The email will contain the patient information forms and will contain a link to a secure [formdesk](#) form
- The link to the [formdesk](#) form will be unique so we will be able to trace from which group (MIS-C, post-COVID condition, controls) the potential participant belongs

Formdesk form

- “Dank voor uw aanmelding. Wij nemen binnenkort contact met u op”
- Form: name, birthdate, address, verify email-address, phone number

Phone call

- Explanation about the study
- Answer questions from the potential participant
- Cases (MIS-C or post-COVID condition): General practitioner.
- Controls: we will ask some questions about prior SARS-CoV-2 to verify that the participant does not exclude as a control
- For cases and controls: country in which the parents and grandparents of the child were born.
- Determine which Saliva Collection Kit is most suitable for their child (assisted collection or self-collection).

Confirmation by email

- “Dank dat u wilt meedoen met de GRIP studie. U ontvangt binnenkort het speeksel-afname setje met het toestemmingsformulier”
- Links to the instruction materials and again to patient information form.

GRIP Saliva Collection Kit by regular mail

- A Saliva collection kit
- A manual on how to use the kit and where to find additional information
- The consent form that parents and/or children need to sign to participate in the GRIP study
- A return envelope

Reminder

- We will send a reminder by email if we have not received the consent form and saliva kit within three weeks
- If we have not received the kit within two to three weeks after the reminder by email, we will phone the potential participants to check if all the materials have been received and verify they still wish to participate

Please read below for additional information on each of the steps.

Recruitment: invitation by email

For this study, we will ask the study coordinators of the already existing studies to approach their participants about participation in the GRIP study (see chapter 3).

This recruitment will take place by e-mail. The e-mail will contain;

- A link to the Patient Information Form about participation in the GRIP study. There will be different forms for the MIS-C/Post-COVID group, and the 'exposed control group';
- A link to our website (www.covidkids.nl/grip) where the participant can find information and a video about the procedures in the GRIP study;
- A link that will refer the participant to a short questionnaire in Formdesk. The link to the formdesk form will be unique so we will be able to trace from which group (MIS-C, post-COVID condition, controls) the potential participant belongs

Formdesk form

If the subject wants to participate in the GRIP study, he/she/the parents can fill out their home address, e-mail address and phone number in this questionnaire. By filling out and returning the questionnaire, the subject consents with our research team contacting the subject by phone for a further explanation on the GRIP study.

Information by telephone

Once we receive a filled out questionnaire, the potential participant of the GRIP study will be contacted by phone. During this phone call:

- We will shortly explain the study
- Subjects can ask additional questions

If the parents/patients wish to participate, we will collect the following information during this phone call:

- For cases (MIS-C or post-COVID condition): General practitioner. This is needed to be able to give feedback on the genetic results.
- For controls: we will ask some questions to verify that the participant does not exclude as a control: (approximate) date of prior SARS-CoV-2 infection(s); how the infection was determined; clinical course of prior SARS-CoV-2 infection(s): exclusion as a control if any of the following apply: admission to hospital; occurrence of MIS-C; persistent health problems related to SARS-CoV-2 infection after 12 weeks
- For cases and controls: country in which the parents and grandparents of the child were born. This information is needed for the interpretation of rare genetic variants.

We will discuss with the parents which type of Saliva Collection Kit is most suitable for their child (assisted collection or self-collection, see next paragraph on saliva collection).

If the subject wants to participate in the GRIP study, we will send him/her/the parents an confirmation e-mail again containing the 'Patient Information Form' and links to the instruction materials. We will send them the 'GRIP Saliva Collection Kit' containing the saliva collection kit and the consent form by regular mail (see next paragraph).

Confirmation email

We will send a confirmation email. In this email, we will again link to the information form and instruction materials.

GRIP Saliva Collection Kit

When a subject want to participate in the GRIP study, we will send the 'GRIP Saliva Collection Kit' to their home address. This package will contain the following materials:

- A Saliva collection kit
- A manual on how to use the kit and where to find additional information (using a QR code and a link to refer them to the instruction video), see also **Appendix A**.
- The consent form that parents and/or children need to sign to participate in the GRIP study
- A return envelope

Children under the age of four years will receive a saliva collection kit for assisted collection, which contains an absorbant sponge. Sample saliva volume for this kit is 0.75 mL.

- advantage of the assisted collection kit: ideal if the donor is not able to spit
- disadvantages of the assisted collection kit: longer collection time (it may take up to 15 minutes to collect enough saliva); more expensive; DNA yield is lower (median yield 17.3 µg)

For children over the age of four years, we will provide a collection kit for self-collection of saliva. Children will need to spit into a funnel to collect the saliva. Sample saliva volume for this kit is 2 mL.

- advantages of the self-collection kit: shorter collection time (2-5 minutes), less expensive, higher DNA yield (median yield 110 µg)
- disadvantage of the self-collection kit: the participant needs to be able to spit into the funnel until the fill line is reached

In the introductory phone call, we will ask the parents of children over the age of four years if they think their child is able to spit into the funnel. If not, the parents/participant will receive the assisted-collection kit.

When the subject has returned the collected saliva and a completely signed consent form, he or she is officially a participant in the GRIP study.

